8.3 Treatment Groups

The following treatment groups will be assessed

Group	Description
Group 1 (Phase 1, n=20)	Standard care with hydrogel KM40C (geko™ XT-3)
Group 2 (Phase 2, n=20)	Standard care with hydrogel KMT10 (geko™ T3)

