3.0 Study Design

The study will be carried out at one clinical site and will be a non-blinded, non-randomised cohort observation study.

The study objective is to compare how well the geko™ device with a new skin adhesive (geko™ XT-3) sticks to the skin compared to that of the adhesive currently used to stick the current device (geko™ T3) to the skin. The performance of the new adhesive is expected to be at least the same if not better than the current one. This is an observational study or cohort study where the performance of the adhesives is observed and rated. There is no intervention to control the performance of the adhesives. As such, a randomized controlled trial is not required as the protocol does not aim to prove a causal relationship between an intervention and adhesive performance.

To enable a direct comparison of performance, patients will be divided naturally into two sequential groups or cohorts. This will also ensure that the XT-3 and T3 devices are not mixed during routine clinical use.

Group 1 patients will be consented and enter Phase 1 of the study. They will continue their treatment pathway with the geko™ T3 device as per hospital clinical protocol for VTE prevention. Group 1 patients will complete the 10-day, study period, before Group 2 patients are consented and enter Phase 2 of the study. Group 2 patients will continue their treatment pathway as per hospital clinical protocol but with the geko™ XT-3 device.

As both the T3 and XT-3 devices are identical in terms of the therapy they deliver to patients, the treatment pathway for both group 1 & 2 patients will be unaffected. The devices differ only in the hydrogel used for adhesion to the skin. Please see Figure. 4 for a schematic of the patient journey.

[figure not shown]

Figure 4: Schematic diagram of the patient journey for Groups 1 & 2.

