6.0 Study Treatments

6.1 Method for Assigning Eligible Patients

The study aims to compare the skin adhesive strength of two hydrogel formulations (new vs current) to ensure that adhesion strength is at least equivalent if not superior

with the new formulation. As such, there is no objective to prove a causal relationship between a treatment and an outcome, therefore patients will be divided naturally into two sequential groups for comparison purposes only. This will also ensure that the T3 and XT-3 devices are not mixed during routine clinical use.

Group 1 patients will enter Phase 1 of the study. They will continue their treatment pathway with the geko™ T3 device as per hospital clinical protocol for VTE prevention. Group 1 patients will complete the 10-day study period, before Group 2 patients are consented and enter Phase 2 of the study. Group 2 patients will continue their treatment pathway as per hospital clinical protocol but with the geko™ XT-3 device.

As both the T3 and XT-3 devices are identical in terms of the treatment they deliver to patients, the treatment pathway for both group 1 & 2 patients will be unaffected. The devices differ only in the hydrogel used for adhesion to the skin.

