Appendix 3: Sample Case Report Forms

Baseline (Day 0)

CASE REPORT FORM	BASELINE (DAY 0)		
STUDY SITE:	THE ROYAL STOKE UNIVERSITY HOSPITAL		
PRINCIPAL INVESTIGATOR:	[name]		
SITE NUMBER	0	2	5
PATIENT NUMBER	0		
PATIENT INITIALS			

Inclusion Criteria (All answers must be YES to include patient in study)

Male or female aged ≥ 18 years	Yes 	No 
Currently an in-patient with diagnosis of acute stroke	Yes 	No 
Use of geko™ as a mechanical prophylaxis strategy for venous thromboembolism	Yes 	No 
Patient understands and is willing to participate in the study and is able to comply with study procedures	Yes 	No 

Exclusion Criteria (All answers must be NO to include patient in study)

Pregnancy or breast feeding	Yes 	No 
Use of neuro-modulation device other than the geko™ device	Yes 	No 
Participation in any other clinical study that may interfere with the outcome of either study	Yes 	No 

Informed Consent

Has the patient freely given written informed consent?	Yes 	No 
Copy given to participant?	Yes 	No 
Date consent signed (DD/MM/YYYY)	____ / ____ / ____	

Patient Profile

Patient Age	18-30 	31-40 	41-50 	51-60 	61-70 	71-80 	Over 81 	
Gender	Male 	Female 						
Date of stroke diagnosis (DD/MM/YYYY)	____ / ____ / ____							
Current mobility - Is patient able to walk independently?	 Yes  No							
Adjunctive treatments (if any)	Drugs 	Stockings 	IPC 	None 				

DAY 0: Application of the geko™ device

Study Phase	geko™ Device Fitted	Lot Number	Expiry Date
Phase 1	geko™ T3		
Phase 2	geko™ X-T3		

CASE REPORT FORM	BASELINE (DAY 0)			DATE (DD/MM/YYYY)
STUDY SITE:	THE ROYAL STOKE UNIVERSITY HOSPITAL			
PRINCIPAL INVESTIGATOR:	[name]			

SITE NUMBER

0	2	5
---	---	---

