-------------------------------	-------------------------------	-------------------------------	-------------------------------	-------------------------------	-------------------------------	-------------------------------	-------------------------------	-------------------------------	--------------------------------	--------------------------------

CASE REPORT FORM	BASELINE (DAY 0)			DATE (DD/MM/YYYY)				
STUDY SITE:	THE ROYAL STOKE UNIVERSITY HOSPITAL							
PRINCIPAL INVESTIGATOR:	[name]							
SITE NUMBER	0	2	5	PATIENT NUMBER	0		PATIENT INITIALS	

Has the patient experienced any Adverse Events since signing the Informed Consent?

Yes No

If yes, please comment below:

CRF completed by:

Print Name: _____ Signature: _____ Date: ____/____/_____

To be completed by Principal Investigator:

I am confident that the information supplied in this case record form is complete and accurate data.

Signature: _____ Date: ____/____/_____

Follow-up Day 1 (please note days 1-9 CRFs will be the same)

CASE REPORT FORM		FOLLOW-UP 1 (DAY 1)			DATE (DD/MM/YYYY)	
STUDY SITE: PRINCIPAL INVESTIGATOR:		THE ROYAL STOKE UNIVERSITY HOSPITAL [name]				
SITE NUMBER		0  2  5 	PATIENT NUMBER	0   	PATIENT INITIALS	

How many hours did the patient wear the geko™ device for?					_____ hours
How well did the geko™ device stick to the patient's leg?					
Very Well Remained attached 	Well Detached in small area 	Poorly Detached over large area 	Very Poorly Detached completely 	Not at all Would not stick at all 	

If any level of detachment has been indicated, please provide a comment below:

Did the patient need any additional fixation to keep the geko™ device in position?				
None 	Micropore Tape 	Adhesive Accessory 	OnPulse™ Knee Strap 	

If removed was the geko™ device easily re-applied?				
Yes 	No 	N/A 		

If no, please comment below:

Overall, how comfortable was the geko™ device for the patient to wear?				

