Very Comfortable 	Comfortable 	Uncomfortable 	Very Uncomfortable 	Extremely Uncomfortable 

If any discomfort has been indicated, please provide a comment below:

Did the patient sleep with the device on?		Yes 	No 
---	--	------------------------------	-----------------------------

DAY 1: Application of geko™ device

Current mobility - Is patient able to walk independently? (If YES is selected patient CANNOT continue in the study - please complete EXIT form)				Yes 	No 
Study Phase	geko™ Device Fitted		Lot Number	Expiry Date	
Phase 1		geko™ T3			
Phase 2		geko™ X-T3			

CASE REPORT FORM	FOLLOW-UP 1 (DAY 1)			DATE (DD/MM/YYYY)	/	/
STUDY SITE: THE ROYAL STOKE UNIVERSITY HOSPITAL	PRINCIPAL INVESTIGATOR: [name]					

SITE NUMBER

0	2	5
---	---	---

 PATIENT NUMBER

0		
---	--	--

 PATIENT INITIALS

--	--

How easy was it to apply the geko™ device to the patients leg?

Very Easy 	Easy 	Difficult 	Very Difficult 	Impossible 
---------------------------------------	----------------------------------	---------------------------------------	--	--

If there were any difficulties, please provide a comment below:

Once applied, how comfortable for the patient was the geko™ device?

Very Comfortable 	Comfortable 	Uncomfortable 	Very Uncomfortable 	Extremely Uncomfortable 
--	---	---	--	---

If any discomfort has been indicated, please provide a comment below:

Which setting was the geko™ device set to?

1 	2 	3 	4 	5 	6 	7 	8 	9 	10 	11 

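### The Section 8.3 group table assigns the two devices to the opposite groups and phases from Sections 3.0 and 6.1 and the case report forms; decoding with it would reverse the sign of XT-3 minus T3

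*Combined protocol and SAP*

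**What the plan says.** Section 8.3 has a two-row table. The row labelled "Group 1 (Phase 1, n=20", closing bracket omitted, is described as "Standard care with hydrogel KM40C (geko™ XT-3". The second row gives Group 2, Phase 2 (also n=20) the current gel and the T3. The current gel is written KMT10 there and KM10T in the earlier sections.

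Section 3.0 says: "Group 1 patients will be consented and enter Phase 1 of the study. They will continue their treatment pathway with the geko™ T3 device". It then says: "Group 2 patients will continue their treatment pathway as per hospital clinical protocol but with the geko™ XT-3 device". Section 6.1 repeats the allocation: "Group 1 patients will enter Phase 1 of the study. They will continue their treatment pathway with the geko™ T3 device", with Group 2 again on the XT-3. Both sections have Group 1 finish its study period before Group 2 is consented.

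In Appendix 3, the table under "DAY 0: Application of the geko™ device" prints Phase 1 beside the T3 and Phase 2 beside the X-T3. The table under "DAY 1: Application of geko™ device" has the same pairing, and a note on that form ("please note days 1-9 CRFs will be the same") extends it to the other follow-up days through Day 9.

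Section 8.1 names the comparison by device. Section 8.4.1 names it by hydrogel and device, then describes it as a comparison of Groups 1 and 2.

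**The concern.** An analyst working from Section 8 needs to know which patients had which gel. The section's only key is the 8.3 table, and it contradicts every other statement of the allocation in the protocol. No text says that device comes from the CRF device field rather than from group or phase.

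The objective in Section 2.0 is directional: the new gel should be no worse than the current one and may be better. A reversed label therefore matters for more than presentation. It would change the sign of the estimated difference and attach the adhesion summaries (8.4.1) to the wrong product. The same applies to the adverse event incidences (8.4.2) wherever they are given by device.

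**Working it through.** **1. The five statements of the allocation, side by side**

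| Place | Group 1 / Phase 1 | Group 2 / Phase 2 |
|---|---|---|
| Section 3.0 | T3 | XT-3 |
| Section 6.1 | T3 | XT-3 |
| Day 0 CRF (phase only) | T3 | X-T3 |
| Day 1-9 CRF (phase only) | T3 | X-T3 |
| Section 8.3 | XT-3 (KM40C) | T3 |

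Four places agree and 8.3 is the exception. Both of its rows are complete, giving group, phase, gel and device, so a broken table does not explain the difference. The amendment history in Appendix 1 records no change of phase order.

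**2. Effect on the estimate**

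Let m1 and m2 be the mean adhesion scores of Groups 1 and 2.

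- Allocation of 3.0, 6.1 and the CRFs: XT-3 minus T3 = m2 − m1.
- Allocation of 8.3: XT-3 minus T3 = m1 − m2 = −(m2 − m1).

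Differences of −0.5, −0.25, 0, +0.25 and +0.5 are read as +0.5, +0.25, 0, −0.25 and −0.5. The number of patients mislabelled is 20 + 20 = 40, which is everyone.

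**3. Effect on conclusions (illustration)**

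The documents give 20 patients per group. They give no margin, SD or numerical coding, so these are assumed: a higher score means better adhesion, observed XT-3 minus T3 d = −0.5 category, margin m = 0.5, SD 0.8 (range 0.6 to 1.0). A two-sample t-test has 20 + 20 − 2 = 38 degrees of freedom, and SE = SD × √(2/20) = 0.8 × 0.316 = 0.253.

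| Reading | Formula for p | Correct label (d = −0.5) | 8.3 label (d = +0.5) |
|---|---|---|---|
| Equivalence (two one-sided tests, TOST) | max[P(T > (d+m)/SE), P(T < (d−m)/SE)] | 0.50 | 0.50 |
| Not worse by more than 0.5 | P(T > (d+m)/SE) | 0.50 | 0.0002 (<0.0001 to 0.0015) |
| Better | P(T > d/SE) | 0.97 (0.994 to 0.939) | 0.028 (0.006 to 0.061) |

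Ranges are for SD 0.6 to 1.0; the entries of 0.50 hold at every SD.

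Since d = −0.5 lies exactly on the assumed margin, a second case away from it is useful. With SD 0.8 and d = −0.8, the 90% confidence interval is −1.23 to −0.37, so non-inferiority is not shown. Decoded through 8.3 it becomes 0.37 to 1.23, which reads as non-inferior and superior. The same reversal occurs at SD 0.4 and 1.2. The TOST verdict is unchanged throughout, because a sign flip only exchanges its two one-sided components.

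**The case against.** The strongest reply is that the harmful path is unlikely. Sections 8.1 and 8.4.1 name the contrast by product. The CRFs have no group field, and phase is recorded only in the same table as the device, lot number and expiry date. An analyst would have to ignore the recorded device, keep the phase and decode it with 8.3. The study is open-label, single-site and sequential, so a complete swap would conflict with every fitting form. The only test named is one of equivalence, which is unaffected if its margins are symmetric. The one-sided p-values belong to tests that Section 8 does not specify, and their inputs are assumed. Section 13.2 refers to a Data Management Plan, not seen here, that might define the device variable. On this view, correcting two table rows is enough.

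Much of this stands. The error is detectable, the equivalence verdict is protected, and the p-values only illustrate what a change of sign can do. It does not dispose of the point. The equivalence test does not protect the estimate, the descriptive summaries, the adverse event attribution or a directional reading of the objective. The CRF field protects the analysis only if the plan says to use it. The Day 10 form also records an adhesion score without any phase or device field, so that score needs either a link to the previous fitting or a key.

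**Conclusion.** The contradiction is real and Section 8.3 cannot stand beside the other four statements. The consequence is conditional: no effect if device is taken from the CRF; all 40 patients mislabelled and the sign of XT-3 minus T3 reversed if it is decoded through 8.3. The sign reversal needs no assumption beyond that decoding. The p-values and intervals rest on the assumed coding, difference, margin and SD, and on directional readings that the statistical section does not define. The point should be fixed before analysis; because the error is detectable and the symmetric equivalence verdict is safe, it does not threaten the study as a whole.

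**What to change.** 1. Reconcile the two rows of the 8.3 table with Sections 3.0 and 6.1 and the CRF device tables, which agree with one another.
2. Add a sentence to 8.4.1: each adhesion score is analysed by the device type recorded on the CRF at the fitting it refers to, not by group number. For a follow-up score taken before the day's new device is fitted, that is the preceding fitting; for Day 10 it is the last recorded fitting.
3. Before analysis, cross-tabulate recorded phase against recorded device and resolve any mismatch from lot numbers and source records.

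The cost is two corrected table rows, a short addition to 8.4.1 and one cross-tabulation. No extra patients, visits or data are needed.

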8.4 Analysis of Study Endpoints

8.4.1 Primary Efficacy Endpoints

The primary efficacy endpoint for the study is:

- the skin adhesion performance of new hydrogel formulation

KM40C used in the geko™ XT-3 device compared to that of the current formulation KMT10 used in the geko™ T3 device. As this is a cohort observation study, this will be a direct comparison between two different patient groups / cohorts (Groups 1 and 2) to evaluate efficacy.

Primary endpoint data from this observational study will be summarised descriptively. Continuous parameters may include mean, standard deviation, median, minimum, and maximum.

8.4.2 Secondary Efficacy Endpoints

The secondary endpoints are:

- The incidence of adverse events (AEs), incidence of serious AEs (SAEs), incidence of study treatment related AEs, and the incidence of investigational device related AEs

Secondary endpoint data from this observational study will be summarised descriptively. Continuous parameters may include mean, standard deviation, median, minimum, and maximum.

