5.2 Premature Withdrawal / Discontinuation

All patients have the right to withdraw at any point without prejudice to their treatment. If necessary, the Investigator may discontinue a patient at any time if it is considered medically necessary e.g. loss of mental capacity. The Investigator may also withdraw a patient if it is considered that the scientific, and therefore, ethical standards of the study are compromised. In addition, patients will be withdrawn from the study, at the Investigator's discretion, if they fail to wear the geko™ device as part of their standard care as directed by the treating physician. The reasons for withdrawal will be fully recorded in the patient's source documents and on the appropriate case report form.

If a participant is prematurely discontinued from the study at any time due to an adverse event (AE) or serious adverse event (SAE), the procedures stated in Section 9.0 must be followed.

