7.4 Application of geko™ Device and Collection of Device Performance Data

Patients will receive treatment with either the geko™ T3 or XT-3 device as part of their standard care for VTE prevention as per hospital clinical protocol. During daily review of the patient by a member of the healthcare team, the following information will be collected for a maximum of 10 days or until the patient is able to mobilize independently:

- Length of time device worn for since fitting (hours)
- Adhesion to patient's leg (score from very well to not at all)
- Use of additional fixation to keep the device in position.
- Patient comfort
- Patient sleep post-fitting
- Patient's current mobility
- Ease with which device fitted (score from very easy to impossible)
- Device setting
- Assess for any AEs

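### Patients leave the study at different times, but the four adverse event endpoints have no time denominator, so unequal stays between the sequential cohorts would distort a per-patient comparison

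*Combined protocol and SAP*

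**What the plan says.** Section 8.4.2 (and 2.1.2) gives four secondary endpoints: "The incidence of adverse events (AEs), incidence of serious AEs (SAEs), incidence of study treatment related AEs", and the incidence of AEs related to the investigational device. The analysis is one line: "Secondary endpoint data from this observational study will be summarised descriptively". The summary statistics named after it suit continuous measures and do not define an incidence.

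Follow-up is variable. Section 7.4 collects data "for a maximum of 10 days or until the patient is able to mobilize independently", and section 4.2 has the same rule. The Day 1–9 form in Appendix 3 enforces it at the mobility question: "If YES is selected patient CANNOT continue in the study - please complete EXIT form". Section 5.2 adds a second route out, withdrawal at the investigator's discretion of patients "if they fail to wear the geko™ device as part of their standard care". The Exit form accepts any last assessment from Baseline to Follow-up 10.

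On allocation, section 3.0 says that "patients will be divided naturally into two sequential groups or cohorts": T3 first, then XT-3.

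Exposure is recorded. The follow-up forms for Days 1 to 10 ask "How many hours did the patient wear the geko™ device for", but no section ties hours worn or days on study to the AE summary.

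**The concern.** A proportion of patients with an event depends on the daily risk and on how long each patient was watched. Randomisation would tend to balance the second factor; here nothing in the design does. Stroke severity, speed of recovery and discharge practice could shift between the two phases, and with them the average stay.

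Section 1.3 gives lower skin irritation as the promise of the new gel, and the instructions for use in Appendix 4 list irritation in the contact area as a side effect. Readers will therefore look at the AE figures for the two gels side by side. If the XT-3 cohort happened to leave sooner, its lower incidence could be taken as support for that promise. If it stayed longer, a higher incidence could be taken as evidence against it. Either could occur with no difference between the gels.

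**Working it through.** **The plan's own figures.** No AE rate is stated, so there is none to reproduce. The only exposure figure is in section 8.2: 4 days of use for 20 patients per phase. (Separately, 20 × 4 × 2 legs = 160 devices, not the minimum of 80 given there; 80 is one device per patient-day. This does not affect the present point.)

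**Inputs.** 20 patients per group (section 3.2), a stay of 4 days as the reference (section 8.2), and a 10-day cap (section 7.4). Assumed, because the documents give neither: a constant daily AE risk *p*, equal in both groups, from 1% to 10%; and a stay of 6 or 8 days in the other group.

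**Step 1: per-patient incidence.** Incidence = 1 − (1 − *p*)^*d* for a stay of *d* days. At *p* = 0.02:

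- 4 days: 1 − 0.98^4 = 7.8%
- 6 days: 1 − 0.98^6 = 11.4%
- 8 days: 1 − 0.98^8 = 14.9%

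Expected patients of 20 are in brackets:

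| Daily risk | 4 days | 6 days | 8 days | Ratio 6:4 | Ratio 8:4 |
|---|---|---|---|---|---|
| 1% | 3.9% (0.8) | 5.9% (1.2) | 7.7% (1.5) | 1.49 | 1.96 |
| 2% | 7.8% (1.6) | 11.4% (2.3) | 14.9% (3.0) | 1.47 | 1.92 |
| 5% | 18.5% (3.7) | 26.5% (5.3) | 33.7% (6.7) | 1.43 | 1.81 |
| 10% | 34.4% (6.9) | 46.9% (9.4) | 57.0% (11.4) | 1.36 | 1.66 |

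With 4 days in both groups the ratio is 1.00 at every risk.

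**Step 2: stays that vary between patients.** Take a constant daily chance of leaving, capped at Day 10. Chances of 0.23 and 0.13 give mean stays of 4.0 and 5.8 days. At *p* = 2% the incidences are 7.7% and 10.8% (ratio 1.41); at 5% they are 17.8% and 24.5% (1.38). The effect does not depend on everyone in a group staying equally long.

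**Step 3: first events per patient-day at risk.** For fixed stays, expected days at risk per patient are [1 − (1 − *p*)^*d*] / *p*. At 2% this is 0.0776/0.02 = 3.88 days for a 4-day stay and 0.1492/0.02 = 7.46 for an 8-day stay. The rates are 0.0776/3.88 and 0.1492/7.46, both 2.0 per 100 patient-days. In the varying-stay runs the rate is likewise 0.020 (or 0.050) in both groups.

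**Step 4: can the forms support this?** In part. The Day 0–9 forms ask a yes/no question about any AE since consent, with a comment box. The answer is cumulative, so the first form marked yes dates the first AE to about a day. Repeated yes answers cannot be counted as separate events, and the forms have no field for onset date, seriousness or relatedness. Table 1 marks AE assessment through Day 10, but the Day 10 list in section 4.3, the Day 10 form and the Exit form have no AE question, so the last wear interval adds time with no matching prompt.

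**The case against.** The strongest reply is that the bias is conditional. Both groups come from one site, under the same eligibility criteria, exit rule and 10-day cap, and sections 3.0 and 6.1 say that the devices deliver identical therapy. Nothing suggests that the gel alters time to mobilisation. A reader might infer that one cohort will look less safe, or that the plan favours XT-3. The documents do not support either: no section predicts a difference in stay or its direction.

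Next, little formal inference is at stake. The objective is adhesion, and AEs are secondary and descriptive, with no test or margin. The size is also modest: even 4 against 8 days at 2% per day is about 1.6 against 3.0 of 20 patients, which chance alone could produce.

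Third, "incidence" is undefined, so a per-patient proportion is a reading. It is the natural one, given the yes/no item, and if something else was meant the text needs to say so.

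Fourth, a reader might infer that events per hour worn, for all four endpoints, would be a free remedy from data in hand. That does not hold. All-cause AEs and SAEs in stroke inpatients need not scale with hours worn, total events cannot be counted reliably from the forms, and the last interval has no AE question. Section 9.1 asks for a full description of device-related events, but that does not fill the gap for all four endpoints.

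All of this limits the point's weight and shapes the remedy. What remains is that variable follow-up, non-random groups and no time denominator leave the AE figures open to distortion that a reader could not detect.

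**Conclusion.** The point holds in conditional form. If the cohorts' stays differ, per-patient incidence will differ with the same daily risk: by a factor of 1.36 to 1.49 for 4 against 6 days, and 1.66 to 1.96 for 4 against 8 days, over assumed daily risks of 10% down to 1%. At 2% per day that is roughly one extra patient in 20, or one to two. If stays are equal there is no distortion.

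The daily risks and the differences in stay are assumptions. The calculation also takes risk to accrue evenly over time; events confined to the first fitting would not be distorted. No planned test or sample size changes. This is a worthwhile improvement to descriptive safety reporting and does not threaten the primary comparison.

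**What to change.** In section 8.4.2:

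- Define incidence as the number and proportion of patients with at least one event, and keep it for all four endpoints.
- Add, for each endpoint, patients with a first event per 100 patient-days at risk, counted from Day 0 to the first daily form that reports the event or, if there is none, to the last AE assessment.
- Show patient-days observed, hours worn and exit reasons by group beside these figures.
- Use hours worn as a supplementary denominator for device-related AEs only.
- State that any descriptive AE comparison of the gels is read alongside these rates.

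In Appendix 3, add AE onset date, seriousness and relatedness fields, and an AE question on the Day 10 and Exit forms, so that events and exposure cover the same interval as Table 1 intends.

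The cost is a small form edit and minor programming. The rate assumes roughly constant risk over time. It does not remove case-mix differences between the cohorts: exit is tied to recovery, so patients who stay longer are the less mobile ones. Both limits should be stated with the results.
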